## 4 INTRODUCTION AND RATIONALE

$\alpha$ -Galactosidase A ( $\alpha$ GAL) is a lysosomal hydrolase enzyme responsible for the metabolism of globotriaosylceramide (GL-3), the enzyme's major glycosphingolipid substrate. In Fabry disease, an inherited deficiency of  $\alpha$ GAL leads to widespread deposition of GL-3, and to a lesser extent other  $\alpha$ -galactoside-containing glycolipids, in the heart(1), kidney(2), liver(3), skin(4), and intestines.(5)

The major clinical signs and symptoms of Fabry disease include skin lesions, benign corneal and lenticular opacities, excruciating acral pain, paresthesias, autonomic dysfunction, cardiac disease, and renal failure.(6) Progressive glycolipid deposition in the microvasculature lead to failure of target organs resulting in death in the third to fifth decades of life prior to the advent of kidney dialysis and renal transplantation. Because the X-chromosome carries the  $\alpha$ GAL gene, most affected patients are hemizygous males, although some heterozygous females can also be affected due to lyonization (random inactivation of 1 X-chromosome).(7)

Fabrazyme® has been approved in more than 40 countries, including the European Union, Australia, Canada, Japan, and the United States (US). Genzyme has manufactured a recombinant form of human  $\alpha$ -galactosidase A (r-h $\alpha$ GAL; agalsidase beta) to provide replacement enzyme to patients with Fabry disease.

More detailed information regarding the preclinical and clinical safety, including a complete listing of adverse events (AEs) and serious adverse events (SAEs), as well as efficacy of Fabrazyme is provided in the Investigator Brochure and/or product labeling.

### 4.1 SUMMARY OF BENEFITS

Immediate benefits for infants enrolled in the study include the possible early diagnosis of Fabry disease, awareness of which can lead to early treatment of the disease. Information collected regarding the potential effects of Fabrazyme on growth and development of infants and lactation of mothers is expected to be useful in planning the use of Fabrazyme therapy for female patients of child-bearing potential.

[figure not shown]
### 4.2 SUMMARY OF RISKS

The r-h $\alpha$ GAL enzyme (Fabrazyme) is a highly purified form of human  $\alpha$ GAL, made by recombinant DNA technology. It is well known that immune response may occur following treatment with exogenous human proteins. In the setting of an endogenous enzyme deficiency, infusion of an exogenous recombinant enzyme to patients' naïve to the normal enzyme is expected to cause antibody response to the enzyme. Of the 177 patients evaluated in 7 clinical studies in which a Fabrazyme dose of 1 mg/kg every two weeks (q2w) was used for the duration of the study, the majority developed IgG (immunoglobulin G) antibodies to Fabrazyme: 84% of 163 males and 43% of 14 females seroconverted. Seroconversion occurred in a mean (SD) time of 194.5 (130.24) days for the 6 females compared to 76.2 (71.16) days for the 124 males. Of the

143 seropositive patients, the majority (a combined total of 66%) exhibit either consistently low titers or declining titers over time. Continued safe treatment with Fabrazyme has not been precluded by IgG antibody development. Across the 7 pooled clinical studies of Fabry patients treated with Fabrazyme 1 mg/kg q2w, the most common drug-related AEs were infusion associated reactions (IARs, defined as drug-related events occurring on the day of the infusion). The most common IARs included chills, pyrexia, nausea, feeling cold, headache, vomiting, paraesthesia, blood pressure increased, flushing, feeling hot, chest discomfort, pruritus, body temperature increased, urticaria, fatigue and somnolence. Most IARs were mild to moderate in intensity and non-serious.

There is no adequate safety data for the use of Fabrazyme in pregnant or lactating women or the possible effects on their infants. It is not known if Fabrazyme passes through the placenta to the embryo or if it is excreted in breast milk. Maternal IgG antibodies may be passively transferred transplacentally or via breast milk to the fetus/infant. Whether maternal administration of Fabrazyme can lead to an IgG and/or IgM (immunoglobulin M) antibody response to Fabrazyme by the fetus/infant is not known.

Some study specific procedures may cause increased risk to the mother or infant, eg, risks associated with phlebotomy include fainting, hematoma, excessive bleeding, or infection.

  
A small number of patients have experienced anaphylactoid reactions some of which were considered life-threatening. Signs or symptoms of possible anaphylactoid reactions have included events of localized angioedema, generalized urticaria, bronchospasm, and hypotension. The risks and benefits of re-administering Fabrazyme following a severe hypersensitivity or anaphylactoid reaction should be carefully considered.

A complete overview of the safety profile of Fabrazyme can be found in the Investigator's Brochure and/or product labeling.

## 5 STUDY OBJECTIVES

The objectives of this study are:

1. To determine whether  $\alpha$ GAL activity is present in the breast milk of mothers with Fabry disease who are being treated with Fabrazyme during lactation.
2. To measure breast milk production and composition (volume, protein and fat content) in women with Fabry disease who receive Fabrazyme during lactation.
3. To determine whether Fabrazyme affects the growth, development, and immunologic response of infants born to mothers with Fabry disease who receive Fabrazyme during lactation.

## 6 INVESTIGATIONAL PLAN

### 6.1 STUDY DESIGN

This is a phase 4, multicenter, multinational study of the effects of Fabrazyme on lactation and on the growth, development, and immunologic response of infants born to mothers with Fabry disease who are treated with Fabrazyme during lactation. There are 3 participation scenarios: mother/infant full participation, mother full participation/infant development only, and mother full participation/infant no participation (see [Section 9.1](#)).

Whether or not the mother continues to lactate will be assessed at each visit. Breast milk will be collected at Months 1, 3, and 6 immediately prior to Fabrazyme infusion, just after the end of the infusion, and 2 hours after the end of the infusion. Breast milk samples will be analyzed for volume, presence of  $\alpha$ GAL activity, total fat content, and total protein concentration. Blood samples from the mother will be drawn for pharmacokinetic (PK) analysis prior to each breast milk collection. If infant genotyping is performed on the umbilical blood cord sample collected at Baseline visit, a buccal cell sample will be obtained from the mother to rule out contamination of the cord blood sample with maternal DNA.

If the parent(s)/legal guardian(s) consent to infant participation, the infant's growth and development will be assessed. The infant may also be tested for the formation or continued presence of serum IgG and IgM antibodies to r-h $\alpha$ GAL and for genotype.

For the purposes of this study, the mother and the infant will each be considered a study patient. The mother must be enrolled in the Fabry Registry and will be followed using the Fabry Registry assessment schedule and CRFs as well as this study's CRF. During this study, infants will be evaluated, ie, the infant may be tested for IgG and IgM antibodies to r-h $\alpha$ GAL at birth and Months 2, 6, and 12 and will be tested developmentally at each visit for 24 months, or until the parent(s)/legal guardian(s) withdraws consent and discontinues the infant's study participation, the infant is discontinued from the study by the Investigator (see [Section 7.3.1](#)), or the study is terminated (see [Section 7.3.2](#)).

If the mother is no longer lactating, the mother will discontinue this study but continue to be followed in the Fabry Registry. The infant will be followed for development only for the remainder of this 24 month study.

### 6.2 STUDY RATIONALE

It is anticipated that with Fabrazyme becoming widely available, more women of childbearing age with Fabry disease will receive Fabrazyme. It is not known whether Fabrazyme is excreted in human milk and there is limited data involving infants of mothers receiving Fabrazyme during lactation. This study is being conducted 1) to determine whether  $\alpha$ GAL is present in the breast milk of mothers with Fabry disease who receive Fabrazyme during lactation; 2) to measure breast milk production and composition (volume and protein and fat content) in women with Fabry

disease who receive Fabrazyme during lactation; and 3) to determine whether Fabrazyme affects the growth, development, and immunologic response of infants born to these mothers. Antibody formation to r-h $\alpha$ GAL in infants will be monitored postpartum for up to 1 year (Month 12). Blood samples for maternal PK analysis will be drawn to assess the clearance of  $\alpha$ GAL postpartum and during the lactating period for up to Month 6. Data on concomitant medications and AEs for both mothers and infants will also be collected at each visit and coded using Medical Dictionary for Regulatory Activities (MedDRA).

### **6.2.1 Dosing Regimen**

Mothers who are receiving Fabrazyme during lactation will continue to receive Fabrazyme treatment (commercially available) during study participation at their prescribed dosage regimen as determined by their treating physician. Each Fabrazyme infusion will be prepared in the standard approved manner (refer to appropriate country labeling information).

### **6.2.2 Study Duration**

This study will last for up to 2 years (24 months).

If the mother is no longer lactating or the mother is no longer receiving Fabrazyme treatment, the mother will discontinue this study but continue to be followed in the Fabry Registry. The infant will be followed, for development only, for the remainder of this 24 month study.

### **6.2.3 Study Population**

Females treated with Fabrazyme while lactating and their infants will be eligible for enrollment into this study. Pregnant women who received Fabrazyme at any point during their pregnancy can be enrolled in the study. If woman is not receiving treatment with Fabrazyme at the Baseline visit, mother should start treatment with Fabrazyme between the delivery and Month 1 visit. Females being treated with Fabrazyme infusion during lactation will have to provide signed written informed consent for themselves and for their infant to participate as study patients prior to any protocol-related procedures being performed.

## 7 PATIENT POPULATION AND SELECTION

Approximately 10 females and up to 10 of their infants (who must be receiving breast milk while the mother is receiving Fabrazyme therapy) will be enrolled in this study, at approximately 10 study centers. Mothers will receive Fabrazyme treatment as part of the standard of care of Fabry disease and will be followed through the Fabry Registry.

### 7.1 INCLUSION CRITERIA

Mothers must meet the following criteria to be enrolled in this study:

1. provide signed written informed consent to participate in this study,
2. be enrolled in the Fabry Registry\* and receiving Fabrazyme while lactating,
3. agree to adhere to the Fabry Registry recommended schedule of assessments for medical history, pregnancy outcome, genotyping, and antibody testing, and
4. agree to adhere to the schedule of evaluations ([Table 1](#), [Table 2](#), or [Table 3](#)) for this study.

\*The Fabry Registry is a global, observational, and voluntary program for patients with Fabry disease, intended to explore and define the natural course and clinical characteristics of the disease as well as to track and characterize response to treatments.

Infants must meet the following criteria to be enrolled in this study:

1. have the signed written informed consent of the parent(s)/legal guardian(s) to participate in this study,
2. be born to a mother who is receiving Fabrazyme during lactation,
3. be receiving breast milk from the mother, and
4. have the agreement of the parent(s)/legal guardian(s) to adhere to the schedule of evaluations ([Table 1](#) or [Table 2](#)) for this study.

### 7.2 EXCLUSION CRITERIA

The mother and infant will be excluded from this study if the mother has received an investigational drug within 30 days prior to study enrollment.

### 7.3 WITHDRAWAL CRITERIA

#### 7.3.1 Patient Withdrawal

The mother (or the legal guardian acting on behalf of the infant and/or the mother) is free to withdraw consent and discontinue her participation as well as the infant's participation in the study at any time, without prejudice to further treatment. The mother and infant's participation in the study may be discontinued at any time at the discretion of the Investigator. The following may be justifiable reasons for the Investigator to remove a patient from the study:

Mother:

- The mother is uncooperative/noncompliant and will not adhere to study responsibilities, including failure to appear at scheduled study visits, or failure to undergo study assessments, and/or failure to comply with the Registry schedule of assessments.
- The mother was erroneously included in the study.
- The mother experiences an intolerable AE.
- The mother stops lactating.
- The study is terminated by the Sponsor.

Infant:

- The mother and/or infant was erroneously included in the study.
- The infant experiences an intolerable AE.
- The study is terminated by the Sponsor.

If the mother and/or the infant discontinues participation in the study, or their participation is discontinued by the Investigator, the mother and/or infant's legal guardian should be contacted by the Study Investigator in order to obtain information about the reason(s) for discontinuation and collection of any potential AEs. Whenever possible the patient should return to the study site for the final clinical assessments as specified in [Section 9.1.1.8](#), [Section 9.1.2.8](#), or [Section 9.1.3.4](#), as appropriate. The Study Investigator will describe the reason for discontinuation on the appropriate CRF.

### 7.3.2 Study or Site Termination

If the Sponsor, Study Investigator, Medical Monitor, or regulatory authorities discover conditions during the study that indicate that the study or study site should be terminated, this action may be taken after appropriate consultation between the Sponsor, Study Investigator, and Medical Monitor. Conditions that may warrant termination of the study or study site include, but are not limited to:

- The discovery of an unexpected, serious, or unacceptable risk to patients enrolled in the study;
- The decision on the part of the Sponsor to suspend or discontinue the study;
- Failure of the Study Investigator to comply with pertinent regulatory authority regulations;
- Submission of knowingly false information from the research facility to the Sponsor, Clinical Monitor, or regulatory authorities; or
- Insufficient adherence to protocol requirements.

Study termination and follow-up will be performed in compliance with the conditions set forth in applicable local regulations and Sponsor Standard Operating Procedures (SOPs).

## 8 STUDY TREATMENTS

### 8.1 TREATMENTS ADMINISTERED

Mothers will receive Fabrazyme treatment (commercially available) at their currently prescribed dosage regimen as determined by their treating physician. The Fabrazyme infusions will be prepared in the standard approved manner (refer to appropriate country labeling information).

### 8.2 INVESTIGATIONAL PRODUCT

#### 8.2.1 Investigational Product Description and Preparation

Description: recombinant human  $\alpha$ -galactosidase A (r-h $\alpha$ GAL; Fabrazyme) is produced by mammalian cell culture technology using a Chinese Hamster Ovary (CHO) cell line.

Chemical Name: recombinant human  $\alpha$ -galactosidase A (r-h $\alpha$ GAL)

CAS Registry Number: 104138-64-9

USAN (WHO/INN): agalsidase beta

Chemical Structure: r-h $\alpha$ GAL is comprised of two subunits of 398 amino acids (approximately 51 kD), each of which contains three N-linked glycosylation sites.  $\alpha$ -galactosidase A catalyzes the hydrolysis of GL-3 and other  $\alpha$ -galactyl-terminated neutral glycosphingolipids, such as galabiosylceramide and blood group B substances to ceramide dihexoside and galactose.

Molecular Weight: r-h $\alpha$ GAL is a homodimeric glycoprotein with a molecular weight of approximately 100 kD.

Commercial Fabrazyme is supplied as a sterile, nonpyrogenic, white to off-white, lyophilized cake or powder for reconstitution with Sterile Water for Injection, USP. Each 35 mg vial contains 37 mg of agalsidase beta, as well as 222 mg mannitol, 20.4 mg sodium phosphate monobasic monohydrate, and 59.2 mg sodium phosphate dibasic heptahydrate. Following reconstitution as directed, 35 mg of agalsidase beta (7 mL) may be extracted from each 35 mg vial. Each 5 mg vial contains 5.5 mg of agalsidase beta, as well as 33.0 mg mannitol, 3.0 mg sodium phosphate monobasic monohydrate, and 8.8 mg sodium phosphate dibasic heptahydrate. Following reconstitution as directed, 5 mg of agalsidase beta (1 mL) may be extracted from each 5 mg vial.

#### 8.2.2 Packaging and Labeling

Commercially supplied Fabrazyme is to be used.

### **8.2.3 Drug Storage**

All drug supplies must be kept in a secure place with restricted access and stored at 2° to 8°C.

### **8.2.4 Study Drug Accountability**

Not applicable.

## **8.3 PATIENT NUMBERING**

After the mother has signed written informed consent for her and her infant to participate, the infant will be assigned a unique 5-digit identification number, which will consist of a 3 digit assigned site number and 2 digit sequential patient number, beginning with 01. The mother's patient identification number will be the number assigned to her through the Fabry Registry.

## **8.4 PACKAGING AND LABELING**

Refer to appropriate country labeling information for packaging and labeling information for Fabrazyme.

## **8.5 PRIOR AND CONCOMITANT MEDICATIONS**

All medications taken by the mother and all medications taken by the infant from the time the Informed Consent Form is signed until the end of study participation will be recorded on the Concomitant Medication CRF.

## **8.6 BLINDING AND RANDOMIZATION**

Not applicable for this open-label study.

## 9 EFFICACY, PHARMACOKINETICS, AND SAFETY VARIABLES

Efficacy will not be measured in this study.

The effects of Fabrazyme treatment on lactation and infants will be monitored continuously throughout study participation and will be assessed in terms of incidence of AEs, concomitant medication, immunogenicity testing, vital signs, and physical examination results including the infant's growth and development. Pharmacokinetics testing will be conducted on the mother's plasma and breast milk.

Refer to [Table 1](#), [Table 2](#), or [Table 3](#) for the schedules of assessments (mother/infant full participation, mother full participation/infant development only, and mother full participation/infant no participation, respectively).

### 9.1 MEASUREMENTS ASSESSED AND STUDY FLOWCHART

After obtaining signed, written informed consent, the study will be conducted as outlined in the following sections. [Table 1](#) summarizes the schedules of study evaluations at each study visit for mothers and infants enrolled for full participation (eg, full/full participation through Month 24). If the mother is enrolled for full participation but the infant is enrolled only for developmental assessments (eg, full/development) (see [Table 2](#)), the mother and infant schedules are the same as full/full participation, except the infant blood samples are omitted. If only the mother is participating in the study (eg, full/no) (see [Table 3](#)), her assessment schedule is the same as full participation except study participation is stopped and considered complete at Month 6. Refer to the Study Operations Manual (SOM) for guidelines regarding test assessments and procedures for handling/shipment of all laboratory samples.

The timing of study procedures will be based on calendar weeks starting with Baseline; defined for the mother as during the month prior to delivery and at birth for the infant. Thus Month 1 is 1 month postpartum. The study procedures and assessments are scheduled so that the maximum time the mother and the infant may participate in the study is approximately 24 months.

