## **11 STATISTICAL METHODS AND PLANNED ANALYSES**

### **11.1 GENERAL CONSIDERATIONS**

Genzyme will be responsible for data entry and editing, reviewing all the information in the CRFs, statistical analysis, and generation of the clinical report.

Clinical data will be double-entered and validated in an Oracle database using Clintrial 4.5.

The Genzyme Biomedical Data and Informatics will perform the statistical analysis of the data derived from this study. The analysis will be performed using the SAS® statistical software system. (9)(10) The status of this study will be summarized annually as part of the Fabry Registry Program Annual Report.

Any missing or invalid data will not be replaced or imputed.

Data collected in this study will be reported using summary tables, graphs, figures, and/or patient data listings.

No hypothesis testing will be performed.

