### **11.2 DETERMINATION OF SAMPLE SIZE**

No formal statistical sample size calculations were performed for this study. The sample size of approximately 10 mothers and up to 10 infants is based upon 1) the availability of mothers to study lactation in this rare disease and 2) the availability of infants whose parents or legal guardians consent to their participation in this study.

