2.3.2 Safety population

The safety population is defined as all patients who enrolled, i.e. signed the informed consent and participated in at least 1 study visit.

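### Lactation and milk-feeding criteria are not confirmed after delivery, and the SAP safety population has no exposure condition, so infants never fed milk from a treated mother count in the objective 3 summaries

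*Protocol*

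**What the plan says.** Protocol 7.1 requires a mother to be "receiving Fabrazyme while lactating". An infant must "be receiving breast milk from the mother, and" have a parent's or guardian's agreement to the visit schedule.

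Protocol 9.1 times everything from Baseline, "defined for the mother as during the month prior to delivery and at birth for the infant". The mother's consent is taken at that visit, and the lactation item there records only her feeding plans (Table 1, footnote f).

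Protocol 6.2.3 describes the eligible population in two ways: women treated while lactating, and pregnant women treated at any time in the pregnancy. It adds: "If woman is not receiving treatment with Fabrazyme at the Baseline visit, mother should start treatment with Fabrazyme between the delivery and Month 1 visit". No consequence is stated if that does not happen.

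Protocol 11.3 analyses all enrolled mothers and infants. SAP 2.3.2 defines the safety population as those who "signed the informed consent and participated in at least 1 study visit". SAP 2.4.5.1 makes that population, split by mother and infant, the denominator for adverse event percentages, and SAP 2.4.5 uses it for all safety analyses. SAP 2.1.4 lists the infant physical examination and Denver II among the safety variables. No exposed or evaluable set is defined.

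**The concern.** Objective 3 asks whether treatment affects infants of mothers treated during lactation. Protocol section 7 says that enrolled infants must be receiving breast milk while the mother is on treatment. The analysis population does not carry that condition. A mother may decide not to breast-feed, fail to lactate or not restart treatment after her antenatal visit. She remains enrolled under the SAP, and so does her infant once seen at birth. The SAP foresees such mothers: its lactation-status item in 2.1.1 allows No as the answer to whether she provides milk for the protocol.

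With about 10 infants, two or three without the exposure under study are a large share of the denominator. A reader of the report would take a clean adverse event table on 10 as evidence about 10 milk-exposed infants.

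**Working it through.** **The plan's own figures.** There is none to reproduce. Protocol 11.2 states "No formal statistical sample size calculations were performed for this study", and 11.1 states "No hypothesis testing will be performed". The planned size is the only input: "The sample size of approximately 10 mothers and up to 10 infants is based upon" availability and consent. The plan reports no intervals; the bound below is used only to show how much reassurance zero events can give.

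**Following one pair through the text.**

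1. The mother consents and attends the antenatal Baseline. Treatment may be present then, but treatment during this lactation cannot be.
2. The infant is seen at birth. Milk status is recorded, but feeding may not have started.
3. Suppose she never lactates, or never restarts treatment. Nothing in the visit lists asks whether the 7.1 criteria are now met.
4. Protocol 6.2.2 takes a mother who is no longer lactating or no longer treated out of the study and keeps the infant in development follow-up for the rest of the 24 months. Not receiving milk is not among the infant's withdrawal reasons in 7.3.1.
5. Both have consent and one visit, so both are in the safety population.

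**Which summaries are touched.** Milk and plasma sampling require lactation and current treatment (Table 1, footnote d; Protocol 9.3), so those results are largely protected. Development-only infants give no blood samples for antibodies (Protocol 9.1, Table 2), and SAP 2.5.3 leaves missing values out of categorical percentages. Most post-birth antibody results are therefore spared too, apart from a possible early sample. What remains is adverse events, growth and Denver II.

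**Zero events.** With n infants and no events, the exact one-sided 95% upper bound is U = 1 − 0.05^(1/n). The number unexposed, k of 10, is an assumption shown over a range:

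| k unexposed | n exposed | U on exposed | U on all 10 |
|---|---|---|---|
| 0 | 10 | 25.9% | 25.9% |
| 1 | 9 | 28.3% | 25.9% |
| 2 | 8 | 31.2% | 25.9% |
| 3 | 7 | 34.8% | 25.9% |
| 4 | 6 | 39.3% | 25.9% |
| 5 | 5 | 45.1% | 25.9% |

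**Non-zero events.** With e events among n exposed and u among k unexposed, the reported rate is (e + u)/10. Take e = 3, n = 8, k = 2, so the exposed rate is 3/8 = 37.5%.

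- u = 0: 3/10 = 30%, below the exposed rate.
- u = 1: 4/10 = 40%, above it.

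The direction depends on events among the unexposed.

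**The reverse case.** A woman already lactating on treatment fits 7.1 and the first sentence of 6.2.3, but cannot complete the antenatal Baseline in 9.1. The only written fallback for a missed Baseline item is infant genotyping at Month 12 (Protocol 9.4.10).

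**The case against.** The strongest reply is that the facts needed are already collected. Lactation and milk-feeding status are recorded at every visit (Protocol 9.4.6), maternal infusions are listed (SAP 2.4.3.1), erroneous inclusion is a reason for removal (7.3.1), and exclusions are decided and documented before lock (10.3). The study is descriptive, has no comparator, and no unexposed patient is documented.

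This stands in part: it makes the repair cheap. It does not supply the rule. Section 10.3 gives no exposure criterion, so any exclusion would be chosen after open-label data are visible, and the SAP states its denominator outright.

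Several stronger readings are tempting and not supported:

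- That all the entry conditions are impossible at Baseline. Section 6.2.3 treats being off treatment then as the exception, and Table 1 records milk feeding at the infant's birth visit.
- That the mothers concerned were never exposed. Section 6.2.3 describes treatment in pregnancy; the accurate term is not exposed during lactation.
- That event rates are pulled towards no effect. The 40% example shows otherwise, and adverse events of any cause are counted.
- That women already lactating are excluded. The only exclusion criterion (7.2) concerns a recent investigational drug, and no text makes a missed Baseline disqualifying.

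**Conclusion.** The point holds as a population-definition gap. Mothers not treated while lactating, and infants who never receive milk from a treated mother, can enter the adverse event denominators; such infants can also enter the growth and Denver II summaries. The text permits this; it does not show that it happens.

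If 2 or 3 of 10 infants were unexposed, zero events on all 10 would suggest an upper bound of 25.9% where the exposed infants support only 31.2% or 34.8%. That rests on the assumed number unexposed and the planned 10. For non-zero events no direction can be claimed.

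A smaller consequence concerns the rule in SAP 2.4 that switches to listings below 5 mothers or 5 infants. It counts those enrolled, so summaries could be issued on fewer than 5 exposed. SAP 2.4.6 has its own sparse-data provision for pharmacokinetics.

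The position of women already lactating is a gap to reconcile, not a stated exclusion.

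**What to change.** 1. **SAP 2.3, before lock.** Add a lactation-exposed set: mothers with at least one postpartum infusion while lactating, and infants recorded as receiving milk after it. Derive it from the visit milk status and the infusion data. Report the objective 3 adverse event, growth and Denver II summaries on this set beside the safety population, not in place of it. Apply the fewer-than-5 rule to the number contributing to each summary. Keep all enrolled mothers for lactation status, so that lactation failure, which bears on objective 2, is not selected out.
2. **Protocol.** Reconcile 6.2.3, 7.1 and 9.1 on when the lactation and milk-feeding criteria are confirmed, and on whether women already lactating may enter. If late entry is considered, note that women joining at Month 3 or 6 are those who sustained lactation.

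The cost is smaller denominators in the exposed set, one extra set of tables and a wording amendment. Because milk status is recorded at visits, feeding that started and stopped between two visits could be missed; the SAP should say how such cases are classified.
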